10. ASSESSMENT OF SAFETY

10.1. Safety Parameters

Safety assessments will include the following:

- AEs/SAEs
- Vital signs
- PE findings
- Clinical laboratory safety assessments
 - Note: Information on cytokines associated with CRS will also be collected as additional safety information but will not be assessed in real time.
- ECG parameters
- Performance status (ECOG) changes

10.1.1. Treatment/Reporting of Overdose or Medication Errors

In the event of an overdose, the Investigator should do the following:

- Contact the Medical Monitor immediately

- Closely monitor the subject for any AE/SAE and laboratory abnormalities
- Obtain a plasma PK sample if requested by the Medical Monitor (determined on a case-by-case basis)
- Document the quantity and duration of the excess dose or error

The Investigator, in consultation with the Medical Monitor, will decide dose interruptions or modifications based on clinical evaluation of the subject.

All overdose cases should be reported as SAEs.

10.2. Adverse Events and Serious Adverse Events

10.2.1. Definition of Adverse Events

An **adverse event** (AE) is any untoward medical occurrence in a study subject. The AE does not necessarily have a causal relationship with this treatment. An AE can therefore be any unfavorable and unintended sign (including a clinically significant abnormal laboratory finding), symptom, or disease temporally associated with the use of a study drug. Adverse events may include the onset of new illness and the exacerbation of preexisting conditions.

Adverse events are classified as “serious” and “non-serious” for regulatory reporting purposes.

10.2.2. Definition of Serious Adverse Events

A **Serious Adverse Event** (SAE) is an AE occurring during study after the subject has signed the ICF that fulfills one or more of the following:

- Results in death
- Is life-threatening; this means that the subject was at immediate risk of death at the time of the event. It does not mean that the event hypothetically might have caused death if it were more severe.
- Requires inpatient hospitalization or prolongation in existing hospitalization
 - Note: Hospitalization is defined as more than 24 hours as an inpatient, or prolongation of planned hospitalization by >24 hours due to an AE.
- Results in persistent or significant incapacity or substantial disruption of the ability to conduct normal life functions
- Is a congenital anomaly or birth defect
- Is an important medical event. Important medical events are events that may not be immediately life-threatening but are clearly of major clinical significance in the opinion of the Investigator. They may jeopardize the subject and may require intervention to

prevent one of the other serious outcomes listed above. Examples of such medical events include allergic bronchospasm requiring intensive treatment in an emergency room or in a physician's office, blood dyscrasias or seizures that do not result in subject hospitalization, and the development of drug dependency or drug abuse.

A distinction should be drawn between serious and severe (Grade 3) AEs. Severity (see [Section 10.2.3.1](#)) is a measure of intensity, whereas seriousness is defined by the criteria above. For example, a mild degree of gastrointestinal bleeding requiring hospitalization for monitoring purposes would be considered an SAE but is not necessarily a severe (Grade 3) SAE. Similarly, an AE that is severe (Grade 3) is not necessarily an SAE. For example, alopecia may be assessed as severe (Grade 3) but would not be considered an SAE.

The following should not be reported as an AE/SAE:

- Signs/symptoms and conditions related to disease progression of the primary condition under the investigation (eg, tumor-related pain, metastasis, new lesions, etc.), hospitalization, and death due to disease progression unless related to study drug.
- Hospitalizations for planned surgical/medical elective procedures or planned admissions for study drug administration.

Suspected Unexpected Serious Adverse Reaction (SUSAR):

During the study, the Sponsor may determine that certain safety reports are required to comply with regulations. The Investigator may receive notification of a Suspected Unexpected Serious Adverse Reaction (SUSAR). These reports must be submitted to the Institutional Review Board (IRB)/Independent Ethics Committee (IEC) per local requirements as soon as possible, and documentation of this submission should be available to the Sponsor or ICON.

10.2.3. Adverse Event Monitoring, Recording, Reporting, Follow-up, and Assessments

AE monitoring will begin upon the signing of the ICF. Concomitant illnesses, which existed prior to entry into the clinical study, will not be considered AEs unless they worsen during the treatment period. Preexisting conditions will be recorded as part of the subject's medical history. A preexisting condition should be recorded as an AE if the frequency, intensity, or character of the condition worsens during the study period.

All AEs experienced by a subject, irrespective of the suspected causality, will be monitored until the event has resolved or stabilized, until any abnormal laboratory values have returned to baseline or stabilized at a level acceptable to the Investigator and Sponsor medical representative, until there is a satisfactory explanation for the changes observed, or until the subject is lost to follow-up.

AEs may be volunteered spontaneously by the study subject, discovered by the study staff during physical examinations, or by asking an open, nonleading question such as "How have you been feeling since you were last asked by us?" or "Have you had any new or changed health problems since you were last here?"

All AE terms (also called reported term or verbatim) should be **recorded** individually. Only a diagnosis, if known, should be recorded as an AE term rather than each individual symptom. If a diagnosis is not available or unclear, all symptoms should be reported.

The recording of AEs will be done in the following manner:

Non-serious AEs will be recorded in the EDC database after signing the ICF through 90 days after the last dose of any study treatment. For screen failed subjects, the recording of non-serious AEs, after the ICF was signed, is not needed.

Serious AEs or SAEs will be recorded in the EDC AE page (eCRF) and the completed SAE report form will be emailed to ICON PVSS. The **Investigator is responsible, within 24 hours of becoming aware of the SAE**, to complete all required details on the initial SAE report form and to email to [REDACTED]

If new information becomes available or details are changed, the submitted SAE form should be retained at the site as is, and a new (blank) follow up SAE report form for the same case should be completed, marked as “follow-up,” and emailed to [REDACTED]. The changes reported in the follow-up SAE report form should be also made in EDC.

Table 17 defines the windows for capturing serious and non-serious AEs.

Table 17: Investigational Site Recording/Reporting of Adverse Events

Type of Adverse Event	Start of Reporting Window	End of Reporting Window
Non-serious AE	Signing of ICF Note: If the subject has failed screening, non-serious AEs should not be recorded.	For non-serious AEs: Any of the following would be considered as the end of reporting: 
 • 90 days after the last dose • initiation of another anticancer therapy • withdrawal of consent by subject
SAE	Signing of ICF	
 • 90 days after the last dose • initiation of another anticancer therapy • withdrawal of consent by subject SAEs related to study drug should be followed up until the resolution, if possible.

AE = adverse event; ICF = informed consent form; SAE = serious adverse event.

ICON PVSS may request clarification of omitted or discrepant information from the initial notification or follow-up SAE report as needed. ICON PVSS and/or the Sponsor may also request additional information regarding the SAE in order to obtain the full clinical picture. The Investigator

or an authorized delegate is responsible for providing the requested information in a Data Clarification Form (DCF) to ICON PVSS/Sponsor.

Initial reports of SAEs must be followed up as soon as possible with detailed information; this may include clear photocopies of other documents as necessary (eg, hospital records, consultant reports, autopsy reports, etc.) with the study subject's personal identifiers redacted. All relevant information obtained by the Investigator through review of these documents will be recorded and forwarded to ICON PVSS within 24 hours of receipt of the information.

SERIOUS ADVERSE EVENT REPORTING INSTRUCTIONS

E-mail: [REDACTED]

Fax number: [REDACTED]

Emergency contact number: [REDACTED] (within US)

[REDACTED] (toll number and outside of US)

1. E-mail your SAE report form to the e-mail address above.
2. Provide the name of the Principal Investigator, your name, the telephone number where you can be reached and the protocol number and title.
3. Immediately forward the SAE report form and any supporting documentation to ICON PVSS; this must be done within 24 hours of becoming aware of the event.

The Investigator is responsible for reporting adverse drug reactions (ADRs) related to the other study treatments to the Sponsor. The Sponsor will report the ADRs to the respective Marketing Authorization Holders, as applicable.

Investigators should perform the following assessments of AEs (both for non-serious and serious):

10.2.3.1. AE Severity/Intensity Grading

The Investigator will assess all AEs for severity, also known as intensity or grades, utilizing the NCI-CTCAE grading scale v5.0 (NCI-CTCAE, 2017). That version will be used for grading AEs, except, as follows:

- a. For CRS and infusion reactions for which the ASTCT CRS Consensus Grading (Table 4; Lee, 2019) will be employed
- b. For immune effector cell-associated neurotoxicity syndrome, the ASTCT ICANS Consensus Grading for Adults (Table 5, Lee, 2019) will be employed.

Note: some grades are not available for certain AEs (eg, Headache can only be Grade 1, 2, or 3; and Sepsis can only be Grade 3, 4, or 5).

AEs **not contained** within CTCAE Version 5.0 will be rated on a 5-point scale as described below (Table 18).

Table 18: Severity Grading Scale

Grade	Description
Grade 1	Mild; asymptomatic or mild symptoms; clinical or diagnostic observations only; intervention not indicated.
Grade 2	Moderate; minimal, local or noninvasive intervention indicated; limiting age-appropriate instrumental ADL ^a
Grade 3	Severe or medically significant but not immediately life-threatening; hospitalization or prolongation of hospitalization indicated; disabling; limiting self-care ADL ^b
Grade 4	Life-threatening consequences: urgent intervention indicated.
Grade 5	Death related to AE.

ADL = activities of daily living.

^a Instrumental ADL refer to preparing meals, shopping for groceries or clothes, using the telephone, managing money, etc.

^b Self-care ADL refers to bathing, dressing and undressing, feeding self, using the toilet, taking medications, and not bedridden

Note: A semi-colon indicates “or” within the description of the grade.

Any change in severity of the AE over a number of days will be captured by recording a new AE, with the amended severity grade and the date (and time, if known) of the change.

When changes in the intensity of an AE occur more frequently than once a day, the maximum intensity for the event should be noted for that day.

It is important to distinguish between serious and severe AEs. Severity is a measure of intensity, whereas seriousness is defined by the criteria under [Section 10.2](#). An AE of severe intensity may not be considered serious.

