4.6.1. Cytokine Release Syndrome

The ASTCT defines CRS as “a supraphysiologic response following any immune therapy that results in the activation or engagement of endogenous or infused T cells and/or other immune effector cells. Symptoms can be progressive, must include fever at the onset, and may include hypotension, capillary leak (hypoxia), and end organ dysfunction” (Lee, 2019).

CRS can present with a variety of symptoms ranging from mild, flu-like symptoms to severe life-threatening manifestations of the inflammatory response. Mild symptoms of CRS include fever, fatigue, headache, rash, arthralgia, and myalgia. More severe cases are characterized by hypotension as well as high fever and can progress to an uncontrolled systemic inflammatory response with vasopressor-requiring circulatory shock, vascular leakage, disseminated intravascular coagulation, and multi-organ system failure (Shimabukuro-Vornhagen, 2018). CRS is more likely to occur after the first dose of plamotamab than subsequent doses, tends to begin somewhat later than hypersensitivity reactions, and is more likely to be associated with hepatic and neurologic complications. Plamotamab associated CRS Symptoms observed in the Phase 1 study include:

- Aphasia or word-finding difficulty
- Arthralgia
- Confusion/mental status changes/delirium
- Serum creatinine increase
- Diaphoresis
- Dizziness
- Dyspnea
- Fatigue (asthenia, lethargy, malaise)
- Fever
- Gait disturbance/dysmetria
- Headache
- Hypotension/hypertension
- Hypoxia
- Myalgia
- Nausea/vomiting
- Rigors/chills
- Tachycardia
- Tachypnea
- Seizures
- Transaminitis/hyperbilirubinaemia
- Tremor

CRS toxicity is defined using the ASTCT CRS Consensus Grading (Lee, 2019). See Table 4 for these definitions.

Table 4: American Society for Transplantation and Cellular Therapy Cytokine Release Syndrome Consensus Grading

CRS Parameter	Grade 1	Grade 2	Grade 3	Grade 4
Fever ^a	Temperature ≥ 38 °C	Temperature ≥ 38 °C	Temperature ≥ 38 °C	Temperature ≥ 38 °C
		With		
Hypotension	None	Not requiring vasopressors	Requiring a vasopressor with or without vasopressin	Requiring multiple vasopressors (excluding vasopressin)
		And/or ^b		
Hypoxia	None	Requiring low-flow nasal cannula ^c or blow-by	Requiring high-flow nasal cannula ^c , facemask, nonrebreather mask, or Venturi mask	Requiring positive pressure (eg, CPAP, BiPAP, intubation and mechanical ventilation)

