BiPAP = bilevel positive airway pressure; CPAP = continuous positive airway pressure; CRS = cytokine release syndrome; CTCAE = Common Terminology Criteria for Adverse Events.

Organ toxicities associated with CRS may be graded according to CTCAE v5.0, but they do not influence CRS grading.

^a Fever is defined as temperature ≥ 38 °C not attributable to any other cause. In subjects who have CRS then receive antipyretic or anticytokine therapy such as tocilizumab or steroids, fever is no longer required to grade subsequent CRS severity. In this case, CRS grading is driven by hypotension and/or hypoxia.

^b CRS grade is determined by the more severe event: hypotension or hypoxia not attributable to any other cause. For example, a subject with temperature of 39.5 °C, hypotension requiring 1 vasopressor, and hypoxia requiring low-flow nasal cannula is classified as Grade 3 CRS.

^c Low-flow nasal cannula is defined as oxygen delivered at ≤ 6 L/minute. Low flow also includes blow-by oxygen delivery, sometimes used in pediatrics. High-flow nasal cannula is defined as oxygen delivered at > 6 L/minute.

Source: Lee, 2019.

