4.6.1.3. Cytokine Release Syndrome Versus Allergic/ Hypersensitivity/ Infusion-related Reactions

CRS is mechanistically different from allergic/hypersensitive/Infusion-related reactions (Brennan, 2010), although some of the manifestations are common to both AEs and both have been reported to occur with therapeutic antibodies. It is less clear how cytokine release is triggered, although it is likely to be associated with immune cell activation; in this case, CD3-expressing lymphocytes may be the prime effector of CRS. See Section 4.6.2 for management of allergic/hypersensitive/infusion-related reactions.

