4.6.2. Allergic/Hypersensitivity/Infusion-related Reactions

Infusion-related reactions have been reported for tafasitamab as well as plamotamab. An allergic reaction is often caused by a type 1 hypersensitivity mechanism due to immunoglobulin E (IgE)-mediated release of histamines and prostaglandins, although a direct interaction with mast cells and basophils can also occur. However, infusion-related reactions, including serious and fatal reactions, are not uncommon with monoclonal antibody therapeutics and tend to occur most frequently during the first few infusions.

Signs and symptoms usually develop during or shortly after drug infusion in hypersensitivity reactions, are more likely to occur after several doses of the drug and are largely related to histamine release. Typical signs and symptoms include rash/urticaria, flushing, pruritus, fever, dyspnea, cough, and hypotension, although the following may also occur ([Lenz, 2007](#)):

- Arthralgia
- Bronchospasm
- Confusion/mental status changes/delirium
- Dizziness
- Fatigue (asthenia, lethargy, malaise)
- Hallucinations
- Headache

- Hypertension
- Myalgia
- Nausea/vomiting
- Rigors/chills
- Diaphoresis
- Tachycardia

Allergic/hypersensitivity/infusion-related reactions are managed according to institutional practices and guidelines. Allergic/hypersensitivity reactions will be defined according to the NCI-CTCAE, Version 5.0 (NCI-CTCAE, 2017) definition of allergic reaction.

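### Infusion reactions are graded on the ASTCT CRS scale, which requires fever at every grade and conflicts with the CTCAE severity endpoint

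*Protocol*

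**What the plan says.** Protocol Section 10.2.3.1 has investigators grade adverse events on CTCAE v5.0 and then qualifies this: "That version will be used for grading AEs, except, as follows". The first exception begins "For CRS and infusion reactions for which the ASTCT CRS Consensus Grading" and points to Table 4.

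Table 4, in Section 4.6.1, repeats "Temperature ≥ 38 °C" under Grades 1, 2, 3 and 4. Hypotension and hypoxia alone separate the grades. The definition of CRS in the same section says that symptoms "must include fever at the onset". Footnote a of the table gives one waiver: once a subject has CRS and has then received antipyretic or anticytokine treatment, "fever is no longer required to grade subsequent CRS severity".

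Other sections treat infusion reactions differently:

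- Section 4.6.1.3: "CRS is mechanistically different from allergic/hypersensitive/Infusion-related reactions".
- Section 4.6.2, whose heading covers allergic, hypersensitivity and infusion-related reactions, says of hypersensitivity reactions: "Typical signs and symptoms include rash/urticaria, flushing, pruritus, fever, dyspnea, cough, and hypotension". It lists bronchospasm among further possible signs and adds: "Allergic/hypersensitivity reactions will be defined according to the NCI-CTCAE, Version 5.0".
- Section 4.2.2 (item 9) and Section 11.8 use CTCAE v5.0 for TEAE severity and make no exception for infusion reactions.

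**The concern.** A severity scale should be able to grade every event assigned to it, and the same event should not be graded on one scale at collection and reported on another. Section 10.2.3.1(a) fails on both counts for infusion reactions that are not CRS. All subjects receive tafasitamab, and Section 4.6.2 says infusion-related reactions are reported with both tafasitamab and plamotamab, so the rule reaches every cohort and arm.

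Three things are at stake: the meaning of the severity recorded for these reactions, the consistency of the TEAE severity summary, and the clarity of rules that act on an infusion-reaction grade. Table 8 in Section 4.7 has infusion-reaction rows for Grades 2, 3 and 4. Section 4.6.2.1 makes the timing of plamotamab depend on whether a tafasitamab reaction is above Grade 1. Section 4.6.1.6 ties rechallenge after CRS and after an infusion reaction to the same grade.

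**Working it through.** No arithmetic applies. The check applies the Section 10.2.3.1(a) rule to the presentations the protocol itself describes.

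1. **Afebrile from onset, with rash, bronchospasm or hypotension, not CRS.** Each column of Table 4 needs at least 38 °C, so none applies. Hypotension would fit the second row of the table, but the fever row is still unmet. Result: no grade.
2. **Febrile, with severe rash or bronchospasm but no hypotension and no hypoxia.** Rash and bronchospasm do not appear in Table 4. Result: Grade 1, whatever their severity.
3. **Fatal infusion reaction.** Section 4.6.2 acknowledges that fatal reactions occur with monoclonal antibodies. Table 4 stops at Grade 4. Result: no matching grade.
4. **CRS already present and treated, fever since resolved.** Footnote a applies and grading continues on hypotension and hypoxia. This is the only case the waiver covers, and it does not reach case 1.

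Two other possible routes to a grade were checked:

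- Table 18 is the fallback for events that CTCAE v5.0 does not contain. It is not written for events that the protocol has moved off CTCAE.
- Section 4.6.2 refers allergic and hypersensitivity reactions to the CTCAE definition. It does not expressly do so for other infusion-related reactions, and nothing says whether it or Section 10.2.3.1 governs when they disagree.

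Case 1 is foreseeable. Sections 7.1.1 and 7.1.2 specify acetaminophen before early infusions, and Section 4.6.1.6 describes acetaminophen as an antipyretic. That premedication may suppress fever in some reactions is an inference. The documents give no frequency for afebrile reactions.

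The sections also disagree on reporting. Section 10.2.3.1(a) has infusion-reaction severity recorded on Table 4, while Sections 4.2.2 and 11.8 report severity for the same events as CTCAE v5.0.

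**The case against.** Four arguments can be made on the other side.

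**CRS remains a separate event.** A reader might infer that sharing a scale contaminates the CRS endpoint, or that Arm B would appear to have CRS. The documents do not support this. The Part 1 primary endpoint is the incidence of CRS and TEAEs (Section 4.2.1); CRS severity is secondary. Section 11.8 summarises events by preferred term and confines its extra CRS analyses to adverse events of CRS. Table 8 has separate rows for the two event types. A Table 4 grade does not recode a tafasitamab reaction as CRS. Section 7.10.1 does word CRS as one kind of infusion-related reaction, and Section 4.6.1.6 handles the two together for rechallenge, but neither changes how CRS is counted. This argument stands.

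**Allergic reactions have a CTCAE route.** This stands in part. Rash, pruritus and bronchospasm are introduced in Section 4.6.2 as signs of hypersensitivity, so for reactions called allergic the defect is two competing rules. The outright gap is the afebrile, non-allergic infusion reaction.

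**Investigators are not left without direction.** The infusion-reaction rows of Table 8 attach the words moderate, severe and life-threatening to their grades. Section 4.6.2 refers management to institutional practice, and Section 4.6.2.2 sends Arm B to the tafasitamab prescribing information. It would therefore be too strong to say that Table 8 cannot be used. None of this names the formal scale, however.

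**The effect on results is minimal.** This stands. SAP Sections 1, 4.1 and 7 report 3 enrolled subjects and listings only. Part 2 required at least 40 evaluated Part 1 subjects before it could open.

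**Conclusion.** The concern holds as an internal contradiction in severity grading. The rule in Section 10.2.3.1(a) gives no grade to a non-CRS infusion reaction that is afebrile from onset, and gives Grade 1 to a febrile one whose severity lies outside hypotension and hypoxia. It contradicts the CTCAE v5.0 severity endpoint and summary, conflicts with Section 4.6.2 for allergic and hypersensitivity reactions, and is hard to square with the distinction drawn in Section 4.6.1.3. The grade-based rules in Sections 4.6.1.6, 4.6.2.1 and 4.7 are left without a clear scale.

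No effect on CRS incidence is shown. The number of reactions affected cannot be estimated, because the documents give no rate of afebrile reactions. For the terminated study the consequence is limited to how severity is read in listings for 3 subjects. It would matter more if the protocol text were reused. The conclusion assumes that Section 10.2.3.1(a) means what it says and that no charter or eCRF guidance outside these documents overrides it.

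**What to change.** - **Section 10.2.3.1(a).** For recording and reporting severity, limit the ASTCT CRS scale to events diagnosed as CRS. Infusion-related reactions then fall under the protocol's own default, CTCAE v5.0, with Table 18 for any event CTCAE does not contain. That matches the TEAE severity endpoint.
- **Sections 4.6.1.6, 4.6.2, 4.6.2.1, 4.7 (Table 8), 10.2.3.1 and 11.8.** Reconcile these so that each states which scale its grades refer to. Because the grades trigger dosing actions, which scale applies in the dosing sections is a clinical decision for the sponsor. No dose, delay, rechallenge or stopping rule is proposed or changed here.
- **Safety listings.** Label the scale used for each CRS and infusion-reaction grade.

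The cost is one revised sentence, a scale reference in each of the other sections, short eCRF completion guidance and a listing footnote. For the terminated study only the listing label is still needed; the rest applies if the protocol text is reused.
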